## 2 Protocol Synopsis

Sponsor	Allergan, Inc.
Study Compound	RST-001 (AGN-151597)
Protocol Number	RST-001-CP-0001
Title	Phase I/IIa, Open-Label, Dose-Escalation Study of Safety and Tolerability of Intravitreal RST-001 in Patients with Advanced Retinitis Pigmentosa (RP)
Phase	1/2a
Indication	Advanced RP
Objective	To evaluate the safety, tolerability and preliminary efficacy of RST-001 in patients with advanced RP. Preliminary efficacy data will be obtained through ocular evaluations.
Study Population	Up to approximately 21 patients will be enrolled in this study.
Study Rationale	
 
First-in-human (FIH) study, designed to evaluate whether RST-001 is safe and well tolerated in patients with advanced RP.
 
This is an open label dose-escalation study of three doses of RST-001
 
To provide further guidance toward the design of a pivotal efficacy study, the study also includes the option to expand, by up to approximately 21, the number of patients
 

Study Design	
 
Structure: Open-label, dose-escalation, non-randomized study
 
Duration: 2 years (with an additional 3 years of long-term follow-up)
 
Treatment: Three doses of RST-001 (low, mid, and high, each group comprising of approximately but no less than three patients) will be evaluated by sequential dose escalation in Phase 1
 
 
Patients will receive a single 100 <math>\mu</math>L intravitreal injection of RST-001 in the study eye. In Phase 2a, approximately 6-12 patients may be enrolled and receive RST-001 at the maximum tolerated dose.
 
The doses used in the study have been calculated from the pre-clinical animal toxicology studies, as follows:
 
 
Low dose = [REDACTED] vg/eye
 
Mid dose = [REDACTED] vg/eye
 
High dose = [REDACTED] vg/eye
 
 
An independent Data Safety and Monitoring Committee (DSMC) will advise on dose-escalation and cohort expansion
 
 
Visit Schedule: 
 
Core study visits: Twelve visits are planned over 24 months including the Screening and Baseline visits, Day 0, Day 1, Day 7, and Months 1, 3, 6, 9, 12, 18, and 24.
 
Long-term follow-up: After completion of the Month 24 visit, each patient will participate in a long-term follow-up study for an additional 3 years to monitor the long-term safety of RST-001. This includes a yearly visit for 3 years (Months 36, 48, and 60).
 
 
 

Key Inclusion Criteria	
Phase 1 and Phase 2a:
 
 
1. Male or female patients, <math>\geq</math> 18 years of age at time of informed consent
 
2. Diagnosis of advanced RP defined as:
 
 

 
Phase 1:
 
 
4. Visual acuity (VA) in the study eye of no-better-than hand motion
 
 
Phase 2a:
 
The DSMC will review the results from Phase 1 to determine if a documented treatment benefit was observed in the patients. If the DSMC identifies a treatment benefit, no changes will be made to the eligibility criteria. If the DSMC does not identify a treatment benefit, VA eligibility criteria will match that of Phase 1 for half of the enrolled patients. VA criteria for the other half of the enrolled patients must range from no-worse-than count fingers to 20/200 vision in the study eye.

Key Exclusion Criteria	
Patients will not be excluded if the molecular diagnosis underlying their advanced RP is not known or if there is presence of macular edema due to advanced RP.
 
However, any one of the following will exclude patients from being enrolled in the study:
 
 
1. Pre-existing eye conditions that would preclude the planned treatment (i.e., injection) or interfere with the interpretation of study endpoints or surgical complications (examples include [but not limited to] glaucoma, diseases affecting the optic nerve causing significant visual field loss, active uveitis, corneal or lenticular opacities);
 
2. Cataract surgery, intraocular and/or peri-ocular injection in the study eye within the prior six months;
 
3. Prior vitrectomy or aphakia in the study eye;
 
4. Known sensitivity to any component of the study treatment or medications planned for use in the study;
 
5. Immunological assays show presence of neutralizing antibodies to AAV2 above 1:1000;
 
6. Use of anti-platelet and anti-coagulants that may alter clotting within 28 days prior to study treatment administration.
 

Justification for dose	
The doses and injection volume of RST-001 have been calculated by allometric scaling from pre-clinical animal studies. Vitreous humor volume was the scaling factor across species. Therefore, the scaling factor of the vitreous volume from mice and dogs to humans is 1:100 and 1:2, respectively. Two nonclinical toxicology studies were conducted in dogs and mice. The safe intravitreal doses in the dog ranged from [REDACTED] vg/eye. In mice, the safe intravitreal doses ranged from [REDACTED] vg/eye. Additionally, two nonclinical pharmacology studies demonstrated efficacy and safety in mice at a dose range of [REDACTED] to [REDACTED] vg/eye in a dose range comparable to the toxicology study. Based on these studies, the expected safe dose range of RST-001 in humans is between [REDACTED] and [REDACTED] vg/eye. In summary, the dose range in this FIH study [REDACTED] is based on the more conservative exposure in the dog, inclusion of potentially efficacious doses, the ability of the manufacturer to concentrate investigational product, and a safe injection volume of 100 <math>\mu</math>L per eye in humans.

Surgical procedure	
A single intravitreal injection of RST-001 in the study eye of patients with advanced RP.

Clinical Study progress	Patients will be enrolled sequentially. The decision to dose escalate will be determined with the DSMC upon review of adverse events (AE), clinical evaluations (ocular and systemic) and laboratory results.
Monitoring of safety and tolerability	Safety monitoring will include a combination of AE reporting, clinical evaluations (ocular and systemic), and laboratory results. Ocular and systemic safety monitoring will include monitoring for signs of an immune response.
Enrollment Stopping rules	Any Grade 3 (Common Terminology Criteria [CTC] for AEs v4.03) or greater AE considered related to the study treatment.
Primary endpoints: Assessment of safety	The primary endpoint is safety at 6 months from start of study treatment. The therapy will be considered safe in the absence of any grade 3 or greater AE considered related to RST-001.
Secondary endpoints	The effect of intravitreal injection of RST-001 in improving visual function as measured by a series of psychophysical, electrophysiological and anatomical measures.
Analysis plan	The sample size for this study was chosen empirically; no formal sample size computations to meet power requirements were made. The sample size of approximately 3 patients for each dose group in Phase 1 are typical for dose escalation studies, an additional up to approximately 12 patients will be enrolled in Phase 2a for further safety and efficacy evaluation. Summary tables and listings of data will be provided per Statistical Analysis Plan. All summaries of categorical data will present frequencies and percentages. All summaries of continuous data will present the number of non-missing values, mean, standard deviation, minimum, median and maximum.

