##### **3.1.2       Clinical features**

Early disease manifests as night-blindness and peripheral visual field defects. As the disease progresses, the visual field constricts relatively symmetrically. Unless complicated by cystoid macula edema, visual acuity (VA) is preserved until advanced disease. A patient with advanced disease will have poor VA and minimal preserved visual field. In some instances, all vision is lost.

Examination findings include abnormal pigmentary changes in the retina, classically appearing as discrete bone-spicules, outer retinal atrophy, optic nerve pallor and retinal vascular attenuation.

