### **5.3.1 Post Injection Medications**

Topical corticosteroid treatment may be given to the injected eye according to the investigator's standard of care.

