### **5.3.2 Management of Post Injection Intraocular Pressure**

The investigator shall have the ability to determine the optimum management of a raised intraocular pressure and may use any combination of topical IOP-lowering medications, oral acetazolamide or anterior chamber paracentesis in order to normalize the intraocular pressure.

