### **6.2.1        Intraocular Inflammation and Immunogenicity Related to RST-001**

During the study, evidence of immune response to RST-001 will be monitored by systemic measurement of humoral and cellular immunity as follows:

These tests will be performed at several timepoints during the study:

There is no diagnostic test available for ocular immunogenicity. Instead, clinical evidence suggestive of immunogenicity will be gathered. Examination findings such as reduced visual acuity in the study eye, intraocular inflammation, uveitis, retinal vasculitis, retinal edema, hemorrhage, exudation and/or detachment will also be gathered. Additional evaluations such as OCT and fluorescein angiography may also aid the clinical identification of an immune response.

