#### **Treatment of intraocular inflammation and immunogenicity**

In the event that immunogenicity is suspected by the investigator, topical, local, intraocular or systemic corticosteroid, corticosteroid-sparing and immunomodulatory therapy may be initiated, usually in an escalating fashion, in accordance with the investigator's practice, to control the inflammation. The patient will continue in the study and all additional assessments and visits will be documented in the source documents.

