10.0 EFFICACY ANALYSES

All analyses will be based on the observed data. *Baseline* for efficacy is defined as the last non-missing efficacy assessment before the first dose of study treatment. All confidence intervals will be 2-sided 95% confidence intervals, unless stated otherwise.

The efficacy parameter will be the change from baseline VA, full field sensitivity, ambulation, object detection discrimination, VEP, ERG, QoL (composite score of NEI VFQ-25 scores) for the study eye at the scheduled Post-treatment visits and will be summarized by visit and by treatment group separately for each phase.

The NEI-VFQ-25 consists of 25 vision-targeted questions that represent 11 vision-related quality of life subscales and one additional general health item. The 11 subscales are general vision (item 2), difficulty with near vision activities (items 5, 6, 7), difficulty with distance vision activities (items 8, 9, 14), limitations in social functioning due to vision (items 11, 13), role limitations due to vision (items 17, 18), dependency on others due to vision (items 20, 23, 24), mental health symptoms due to vision (items 3, 21, 22, 25), driving difficulties (items 15c, 16, 16a), limitations with peripheral vision (item 10), limitation with color vision (item 12), and ocular pain (items 4, 19). The general health item is item 1.

Responses to individual questions are recoded to scores using the following scoring system, with a higher score representing better functionality. For example, for question 1, a score of 100 is applied for a response of “1.” The summary score for each subscale is determined by taking the average across multiple items within each corresponding subscale. For subscales calculated based on multiple questions, at least one non-missing response is required (i.e., at least one question is answered). The overall composite score is then calculated by averaging over all 11 vision-targeted subscale scores, excluding the general health score. Items or subscales that are left blank are excluded from the calculation of average scores; e.g., if any of the 11 subscale scores is missing, the overall composite score will be calculated based on the mean of the non-missing subscales.

Table 10-1 VFQ-25 Coded Values for Each Item

Items	Response Level	Coded value
1, 3, 4, 15c ^a	1	100 (best)
	2	75
	3	50
	4	25
	5 ^b	0 (worst)
2	1	100 (best)
	2	80
	3	60
	4	40
	5	20
	6	0 (worst)
5-14, 16, 16a	1	100 (best)
	2	75
	3	50
	4	25
	5	0 (worst)
	6	Missing

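### Eyes with RP macular edema are admitted, but the SAP's only examination-findings summary cannot count new macular fluid or separate it from edema present at entry

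*Protocol*

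**What the plan says.** **Entry.** The Synopsis, and again Protocol 3.15.3.2, state that a patient is not excluded if the molecular diagnosis is unknown "or if there is presence of macular edema due to advanced RP". Protocol 3.1.2 names such edema as an exception to preserved vision: "Unless complicated by cystoid macula edema, visual acuity (VA) is preserved until advanced disease".

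**Safety.** Protocol 6.2.1 says there is no diagnostic test for ocular immunogenicity, so suggestive clinical evidence is collected instead. The list includes "retinal vasculitis, retinal edema, hemorrhage, exudation and/or detachment will also be gathered". It does not say how edema already present at entry is to be told apart.

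**Treatment after injection.** Protocol 5.3.1: "Topical corticosteroid treatment may be given to the injected eye". For raised intraocular pressure (IOP), Protocol 5.3.2 says the investigator "may use any combination of topical IOP-lowering medications, oral acetazolamide or anterior chamber paracentesis". For suspected immunogenicity, Protocol 6.2.1 says "topical, local, intraocular or systemic corticosteroid, corticosteroid-sparing and immunomodulatory therapy may be initiated", and the patient stays in the study.

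**Analysis.** SAP Table 11.4-2 lists intraretinal and subretinal fluid among the macular findings and marks severity as not applicable for the whole macula row. Apart from IOP and cup/disc ratio, the only tabulation in SAP 11.4 counts patients with a rise of over one grade from baseline. SAP 8.0 does not name macular edema among the baseline characteristics. Under SAP 10.0, change in visual acuity (VA) and the other function measures "will be summarized by visit and by treatment group separately for each phase".

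**The concern.** The trial's primary objective is safety, and the dog study (Protocol 3.6.2.1) found dose-related ocular inflammation. New fluid at the macula is therefore something the safety tables should show. Because eyes with edema are let in, fluid seen after injection may have been there before or may be new. The reader needs to know which, by dose group.

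The plan collects what is needed but does not report it in a usable form. The gap is wider after Month 24: Protocol Table 3 schedules VA and a complete ophthalmic examination but no SD-OCT, so in long-term follow-up the examination is the only scheduled look at the macula.

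There is a smaller efficacy point. The protocol itself links edema to acuity, so an acuity change that coincides with a change in macular fluid should be visible as such.

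**Working it through.** **1. Group sizes.** Protocol Table 1 gives three dose groups of 3 and a Phase 2a of 6 to 12. 3 × 3 + 12 = 21 reproduces the stated maximum of about 21; 3 × 3 + 6 = 15 if a benefit is identified.

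**2. The SAP 11.4 rule applied to each kind of finding.** A finding is counted when (later grade − baseline grade) > 1. Fluid has no grade. The table gives it the most favorable reading, absent = 0 and present = 1, which the SAP does not state.

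| Finding | Baseline | Later | Change | Counted? |
|---|---|---|---|---|
| Anterior chamber cells (graded, for contrast) | +1 | +3 | 3 − 1 = 2 | Yes |
| Macular fluid, new | absent (0) | present (1) | 1 − 0 = 1 | No |
| Macular fluid, present throughout | present (1) | present (1) | 1 − 1 = 0 | No |
| Macular fluid, resolved | present (1) | absent (0) | 0 − 1 = −1 | No |

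Taken literally, with no grade, the change is undefined and nothing is counted. Under either reading all three fluid patterns give the same entry: zero.

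**3. Size of one missed eye.** 1/3 = 33% in a Phase 1 dose group, 1/6 = 17% or 1/12 = 8% in Phase 2a. Each would appear as 0%.

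**4. How often edema at entry would arise.** The documents give no prevalence. Assume p = 10% to 50%. The chance of at least one such study eye among n is 1 − (1 − p)^n.

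| n | p = 10% | p = 50% |
|---|---|---|
| 3 (one dose group) | 1 − 0.9³ = 27% | 1 − 0.5³ = 88% |
| 9 (Phase 1) | 1 − 0.9⁹ = 61% | 1 − 0.5⁹ = 99.8% |
| 21 (maximum total) | 1 − 0.9²¹ = 89% | over 99.9% |

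**5. Other outputs that might fill the gap.**
- SD-OCT (SAP 11.2, 11.3): a qualitative reading of change; no fluid or edema category is named.
- Ocular medical history (SAP 8.0): may mention known edema, but is not a baseline scan reading.
- Concomitant ocular drugs by eye (SAP 8.0): tabulated, but not tied to fluid or outcome.
- Adverse events (SAP 11.1): compared with pre-dose severity, but fluid enters only if the investigator reports it as an event.

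None of these states fluid as present at baseline, new or resolved, and none sets it beside VA at the same visit.

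**The case against.** The strongest reply is that the data are not lost. SD-OCT change is a primary safety measure at Month 6, fluid is a prespecified finding, ocular history and drugs are summarized, and new edema may be reported as an adverse event. With about 21 patients, a careful reader could join these by hand from listings. SAP 15.1 gives a general rule for counts and percentages, and the table shells, in a separate document, may apply it to fluid. The advanced RP definition and Protocol 11.3.5 are also withheld, so an edema item there cannot be ruled out.

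Much of this stands. It would be wrong to say that edema goes unobserved. But SAP 15.1 says how categorical data are shown, not which tables are made, and SAP 11.4, which does say so, has a rule that fluid cannot meet. Joining listings by hand is not a prespecified safety summary.

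A reader might go further and infer that edema change, driven by corticosteroid or acetazolamide, will pass for gene-therapy benefit or harm in the group efficacy means. The documents do not support that:
- They do not say that these drugs alter RP edema, and acetazolamide is named only for raised IOP.
- Phase 1 study eyes have hand motion or worse. Protocol 11.3.4 lets acuity at that level be shown as categories, and no visible rule turns these into letters, so a letter mean in a group of 3 has no basis.
- Eyes with count fingers to 20/200 vision enter only if the DSMC finds no benefit in Phase 1. The SAP does not summarize those 6 apart from the rest of Phase 2a.
- Protocol 3.1.2 ties edema to acuity, not to full field sensitivity, ambulation or visual evoked potentials.

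**Conclusion.** The point holds as a gap in safety reporting. As SAP 11.4 is written, new macular fluid in a study eye cannot appear in the examination-findings summary, and no visible output distinguishes it from edema present at entry. One affected eye is 33% of a Phase 1 dose group and would show as zero. That follows from the rule itself and needs no assumption about prevalence or drug effect. It does take intraretinal and subretinal fluid as the recorded form of macular edema.

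The efficacy side is limited to a missing link in the listings, relevant mainly to any Phase 2a eyes with count fingers to 20/200 vision. Any effect of post-injection drugs on edema, and the 10% to 50% prevalence range, are assumptions. The table shells and some text could not be seen.

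**What to change.** 1. **SAP 11.4.** For the ungraded macular findings, tabulate the number and percent of study eyes with fluid present at baseline, new after treatment, and resolved, by treatment group and phase. Baseline is the last pre-dose value, as in SAP 11.0. State the source (examination or SD-OCT) so that like is compared with like.
2. **SAP 8.0.** Add study-eye macular edema at baseline, yes or no, from the Screening/Baseline SD-OCT.
3. **SAP 10.0 and 11.2.** In the patient listings, show macular fluid status beside VA change at the same visit, as supportive information, chiefly for any Phase 2a eyes with count fingers to 20/200 vision.

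Do not add a repeat summary that leaves out visits where fluid status has changed. That would condition on something that happens after treatment. If RST-001 causes inflammatory edema, it would remove the harmed eyes, including from the primary safety summary, and one eye is a third of a Phase 1 group.

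Cost: a few table rows, one baseline flag and one listing column, from examinations already scheduled. No clinical procedure changes. SAP 4.0 still follows Protocol Amendment 2 and the protocol is now at Amendment 4, so this can go into the same revision before database lock.

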### **3           Introduction**

#### **3.1           Background and Rationale**

##### **3.1.1       Retinitis pigmentosa (RP)**

Retinitis pigmentosa (RP) is a hereditary, slowly-progressive, neurodegenerative disease of the retina. It is estimated that the prevalence of RP in the United States (US) is approximately 100,000 individuals ([Sohocki et al., 2001](#)) with 10-20% suffering severe vision loss from this condition. A similar prevalence rate is thought to occur worldwide. RP is most frequently inherited as an isolated ocular disease though it is a manifestation of many syndromes.

RP is genetically heterogeneous with more than forty causative genes and perhaps only 50% of genes have been identified. In the US, RP is most commonly inherited as an autosomal dominant trait.

##### **3.1.2       Clinical features**

Early disease manifests as night-blindness and peripheral visual field defects. As the disease progresses, the visual field constricts relatively symmetrically. Unless complicated by cystoid macula edema, visual acuity (VA) is preserved until advanced disease. A patient with advanced disease will have poor VA and minimal preserved visual field. In some instances, all vision is lost.

Examination findings include abnormal pigmentary changes in the retina, classically appearing as discrete bone-spicules, outer retinal atrophy, optic nerve pallor and retinal vascular attenuation.

##### **3.1.3       Cellular pathology**

RP is primarily a disease of the rod photoreceptors which are gradually lost as the disease progresses ([Daiger et al., 2007](#)). Cone photoreceptors subsequently degenerate, together with the retinal pigment epithelium. Loss of the photoreceptors results in changes in the inner retina, which include cell reorganization, disorganization and cell loss. Even in the advanced stages, retinal ganglion cells, which comprise the innermost layer of the retina, persist and maintain their connections with the brain.

##### **3.1.4       Pathogenesis**

Given the large number of causative genes and the diverse properties of the proteins they encode, the precise molecular pathology of RP remains elusive. It is likely that the molecular pathology stresses the photoreceptor cells eventually resulting in the activation of cell death pathways.

Photoreceptors and other neuronal cells of the retina have little or no replicative function and cell loss results therefore in progressive deficit.

### **3.1.5 Treatment**

Currently, there is no approved drug treatment for RP. Supplemental doses of Vitamin A may reduce the rate of degeneration in certain individuals but the effects are insubstantial ([Rayapudi et al., 2013](#)). The Argus II retinal prosthesis (an opto-electronic implant developed by Second Sight Medical Products Inc., Sylmar, CA) has been approved by the FDA, on a humanitarian basis, for those most severely affected by RP ([Dorn et al., 2013](#)).

## **3.2 Adeno-Associated Virus**

Adeno-associated virus (AAV) is a parvovirus with a single-stranded DNA genome ([Muzyczka N, Berns KI, 2001](#)). It requires a helper virus to complete its replication cycle in culture and in humans ([Blacklow NR, Hoggan MD, 1967](#)). AAV does not appear to integrate in humans ([Schnepp BC, et al 2005](#)) and has not been associated with human disease ([Flotte TR, Carter BJ, 1995](#)).

